2.7.1 Adverse events (AEs)

All the summary tables for adverse events (AEs) will be tabulated by randomized groups. AE summaries will include all AEs occurring during the on-treatment period. All AEs collected in the AE eCRF page will be listed along with the information collected on those AEs e.g. AE relationship to study drug, AE outcome, etc. AEs with start date outside of the on-treatment period will be flagged in the listings.

AEs will be summarized by number and percentage of subjects having at least one AE, having at least one AE in each primary system organ class (SOC) and for each preferred term (PT) using MedDRA coding. A subject with multiple occurrences of an AE will be counted only once in the respective AE category. A subject with multiple CTCAE grades or the same preferred term will be summarized under the maximum CTCAE grade recorded for the event. AE with missing CTCAE grade will be included in the 'All grades' column of the summary tables.

In AE summaries, the primary system organ class will be presented alphabetically and the preferred terms will be sorted within primary SOC in descending frequency. The sorting order for the preferred term will be based on their frequency in the asciminib 40 mg b.i.d. group.

The following adverse event summaries will be produced: overview of adverse events and deaths, AEs by SOC and PT, summarized by relationship, seriousness, leading to treatment discontinuation, leading to dose interruption/adjustment, requiring additional therapy, and leading to fatal outcome. The study treatment-related AEs/SAEs/AEs leading to treatment discontinuation as well as SAE with fatal outcome are summarized for the corresponding Safety set.

For posting to ClinTrial.gov and EudraCT, a summary table of on-treatment deaths and serious AEs and another summary table of non serious AEs, both including occurrences (an occurrence is defined as >1 day between start and prior end date of record of same preferred term) and sorted by SOC and PT, will be presented as well.

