6.6.2 Dose escalation

For patients not in MMR at 48 weeks or losing the response after the week 48 assessments up to week 108, a dose escalation to 200 mg q.d. may be considered for patients on 40 mg b.i.d. or 80 mg q.d., if in the investigator's opinion the patient may benefit from the escalation. In addition, there must not be any grade 3 or 4 toxicity while on therapy, or persistent grade 2 toxicity, possibly related to asciminib and unresponsive to optimal management.

Patients with dose reduction to 40 mg due to side effects may receive a dose escalation to 200 mg daily if the event requiring the dose reduction has disappeared and the patient has been treated at least 3 months on the standard dose of 80 mg.

CCI [REDACTED] will be performed in patients not reaching MMR at 48 weeks or patients losing the response after the week 48 assessments up to week 108, and for whom a dose escalation might benefit the patient, to identify potential BCR-ABL mutations that could confer resistance to asciminib. With the limited information on mutations no general treatment recommendations can be given for individual mutations.

Dose escalation may be performed at week 60 for patients not in MMR at week 48. For patients losing the response after week 48 up to week 108, dose escalation may be performed up to week 120 after confirmed loss of MMR in 2 consecutive tests and CCI [REDACTED] results are available.

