2.1 Data analysis general information

The planned analyses will be performed by Novartis. SAS version 9.4 or later will be used to perform all data analyses and to generate tables, figures and listings.

No formal interim analysis is planned for this trial. The following analyses are planned as detailed below.

- 48-week primary analysis: Formal testing of the primary endpoint will be performed. Analyses of other efficacy endpoints at and by week 48 and safety analyses will also be performed.
- 96-week analysis: Analyses of efficacy endpoints at and by week 96 and safety analyses will be performed.
- End of study treatment analysis is similar to the 96-week analysis without formal statistical testing. All efficacy and safety analyses will be included.

Except where categorically stated, all analyses, including the primary analysis will be conducted on **all** participant data (excluding the additional subjects who were intolerant to the last TKI and were in MMR at baseline). The purpose of having two randomized groups is not for comparison, but to provide data on different dosing regimens. Randomization is only used to have a balance in the allocation of treatment into either asciminib 40 mg b.i.d. or 80 mg q.d.

Data included in the analyses

The analysis data cut-off dates for the planned analyses are:

- 48-week Primary analysis: After all randomized subjects have been on study treatment for 48 weeks or discontinued earlier, i.e., LPFT + 48 weeks.

- 96-week analysis: After all randomized subjects have been on study treatment for 96 weeks or discontinued earlier, i.e., LPFT + 96 weeks.
- End of study treatment analysis: 30 days after the EOsT. (Note: After the study treatment period, every effort will be made to continue provision of the study treatment to subjects who in the opinion of the investigators are still deriving clinical benefit through alternative options if asciminib is not commercially available).

All statistical analyses will be performed using all data collected in the database up to the respective data cut-off date. All data with an assessment date or event start date (e.g. vital sign assessment date or start date of an adverse event) prior to or on the cut-off date will be included in the analysis. Any data collected beyond the cut-off date will not be included in the analysis and will not be used for any derivations.

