2.1.1 General definitions

Investigational drug and study treatment

Investigational drug, will refer to asciminib. No additional treatment beyond investigational drug is included in this trial.

Treatment groups

- Asciminib 40 mg b.i.d. (Subjects randomized to asciminib 40 mg b.i.d. at the beginning of the study)
- Asciminib 80 mg q.d. (Subjects randomized to asciminib 80 mg q.d. at the beginning of the study)

The standard dose for all subjects in this study is asciminib 40 mg b.i.d. or 80 mg q.d. For subjects not achieving MMR at 48 weeks or losing the response after the week 48 assessment up to week 108, a dose escalation to 200 mg q.d. may be considered per investigator decision.

Date of end of study treatment (EOsT)

The EOsT date is the date that the study treatment is ended for the entire study. On this date, subjects are treated for at maximum 144 weeks, unless subjects have discontinued study treatment earlier.

Date of first administration of study treatment

The date of first administration of study treatment is derived as the first date when a non-zero dose of study treatment was administered as per the Study Treatment electronic case report form (eCRF). The date of first administration of study treatment will also be referred as start of study treatment.

The date of first administration of study treatment is the same as the date of first administration of investigational drug.

Start Date of dose escalation

The start date of dose escalation is derived as the first date when a subject had dose escalated to 200 mg q.d. of study treatment as per the Subject Status Dose Escalation case report form (eCRF).

Date of last administration of study treatment

The date of last administration of study treatment is defined as the last date when a non-zero dose of study treatment was administered as per Study Treatment eCRF.

The date of last administration of study treatment is the same as the date of last administration of investigational drug.

Study day

The study day, describes the day of the event or assessment date, relative to the reference start date.

The study day is defined as:

- The date of the event (visit date, onset date of an event, assessment date, etc.) – reference start date + 1 if event is on or after the reference start date;
- The date of the event (visit date, onset date of an event, assessment date, etc.) – reference start date if event precedes the reference start date.

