2.7 Safety analyses

For all safety analyses, the Safety set (SAF, SAF 2) will be used, except where stated otherwise.

Safety summaries (tables, figures) include only data from the on-treatment period with the exception of baseline data which will also be summarized where appropriate (e.g. change from baseline summaries). In addition, a separate summary for death including on treatment and post treatment deaths will be provided. In particular, summary tables for adverse events (AEs) will summarize only on-treatment events, with a start date during the on-treatment period (treatment-emergent AEs).

The overall observation period will be divided into three mutually exclusive segments:

1. Pre-treatment period: from day of participant's informed consent to the day before first dose of study medication
2. On-treatment period: from day of first dose of study medication to 30 days after last dose of study medication
3. Post-treatment period: starting at day 31 after last dose of study medication.

The following will also be summarized for a) **all** subjects using combined sets (SAF and SAF 2), for b) SAF 2 only, for c) subjects by dose escalation status (with or without dose escalation) and for d) only for subjects with dose escalation (prior to and after dose escalation):

- All deaths
- Serious adverse events and adverse events of special interest
- Adverse events leading to treatment discontinuation
- Grade 3 and 4 adverse events

Analysis of ECG data, for dose escalation is mentioned in [section 2.7.4.1](#).

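### The main by-regimen AE tables, and any by-regimen laboratory worst-value tables, count events that start after escalation to 200 mg q.d. under the starting 40 mg b.i.d. or 80 mg q.d. regimen; a pre-escalation version should be added

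*SAP*

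**What the plan says.** **Main AE tables.** SAP 2.7.1 states: "All the summary tables for adverse events (AEs) will be tabulated by randomized groups". It adds: "AE summaries will include all AEs occurring during the on-treatment period". A subject with several grades of the same term "will be summarized under the maximum CTCAE grade recorded for the event". Protocol 12.5.2 also calls for AE tables by randomized group.

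**Groups.** SAP 2.1.1 fixes them at randomization, for example "Asciminib 40 mg b.i.d. (Subjects randomized to asciminib 40 mg b.i.d. at the beginning of the study". It defines no 200 mg group.

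**Window.** SAP 2.7 defines it as "On-treatment period: from day of first dose of study medication to 30 days after last dose of study medication". Escalation does not close it.

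**Escalation.** Protocol 6.6.2 says: "Dose escalation may be performed at week 60 for patients not in MMR at week 48". SAP 1.1 puts the last permitted start at Week 120 and caps treatment at 144 weeks.

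**Cut-offs.** SAP 2.1 sets the primary cut-off at LPFT + 48 weeks and the next at LPFT + 96 weeks, and states: "All statistical analyses will be performed using all data collected in the database up to the respective data cut-off date".

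**Existing escalation summaries.** SAP 2.7 adds summaries by escalation status and "only for subjects with dose escalation (prior to and after dose escalation"). They cover deaths, SAEs and AESIs, AEs leading to treatment discontinuation, and grade 3/4 AEs. SAP 2.7.4.1 does the same for ECG. SAP 2.3.1 and 2.4.1 give separate disposition summaries for escalated subjects.

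**The concern.** SAP 2.1 says the two arms exist to yield information about each way of giving 80 mg a day, not to be compared. Protocol 1.2 expects the descriptive results to guide patient management. A reader will take a column headed 80 mg q.d. as the safety profile of that regimen. For an escalated patient, part of that column reflects time at 2.5 times the daily dose (200/80). A worse grade recorded on 200 mg also replaces the grade the patient had on 80 mg.

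The SAP already recognizes the switch elsewhere. In SAP 2.4.1 the planned cumulative dose is 80 mg/day before escalation and 200 mg/day after it. The main AE tables and laboratory worst-value summaries do not follow that split.

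**Working it through.** **1. Design figure.** The only stated design figure is 80% power (SAP 3: N = 156, 23% against 33%, one-sided 0.025). By exact binomial calculation the smallest rejecting count is 47/156, with alpha 0.0241 and power 0.801. The figure is reproduced, and this point does not depend on it.

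**2. Tracing one event.** A patient randomized to 80 mg q.d. escalates at Week 60 and has a new grade 2 event at Week 70.
- Group: 80 mg q.d., fixed at randomization (SAP 2.1.1).
- In the window: yes, because study drug continues (SAP 2.7).
- Main table (SAP 2.7.1): counted under 80 mg q.d.
- Escalation tables (SAP 2.7): not shown, unless the event is serious, an AESI or leads to discontinuation.

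**3. Which summaries are split by escalation**
- Split, but not stated to be by regimen: deaths, SAEs and AESIs, AEs leading to discontinuation, grade 3/4 AEs (SAP 2.7).
- Split: ECG (SAP 2.7.4.1).
- Not split: all-grade AEs by SOC and PT, treatment-related AEs, AEs leading to dose interruption or adjustment, AEs requiring additional therapy, and the non-serious AE table for public posting (SAP 2.7.1).
- Not split: worst post-baseline grade, shift to worst on-treatment value, and worst liver values (SAP 2.7.3). That section does not state its columns, so the point applies to any by-regimen presentation of them.

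**4. Post-escalation time per patient**
- Escalation at Week 60: 144 − 60 = 84 weeks; 84/144 = 58%.
- Escalation at Week 120: 144 − 120 = 24 weeks; 24/144 = 17%.

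These are ceilings for patients who stay on 200 mg to Week 144.

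**5. Exposure at each cut-off.** Take LPFT as the last patient's first treatment, and consider a patient who started d weeks before that. The most post-escalation time at the cut-off is:
- LPFT + 48: (48 + d) − 60 = d − 12 weeks, so none unless d exceeds 12.
- LPFT + 96: (96 + d) − 60 = 36 + d weeks, capped at 84.
- End of study treatment: up to 84 weeks.

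The amendment rationale reports 91 patients randomized and treated by 10 August 2022, against about 186 planned. Entry was therefore staggered, but accrual dates are not given.

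**6. Illustration with assumed rates.** Let p be the incidence on 80 mg, f the share of a regimen that escalates, and q the share of escalated, still event-free patients whose first event falls after escalation. Tabulated incidence = p + f(1 − p)q. Assume f = 10–40% and q = 10–30%. The values of p are phase III asciminib figures from Protocol 1.1, used only as base rates.

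| Base p | Lowest | Highest |
|---|---|---|
| 17.3% (thrombocytopenia, grade 3 or worse) | 0.173 + 0.1×0.827×0.1 = 18.1% | 0.173 + 0.4×0.827×0.3 = 27.2% |
| 50.6% (grade 3/4 AEs) | 0.506 + 0.1×0.494×0.1 = 51.1% | 0.506 + 0.4×0.494×0.3 = 56.5% |
| 89.7% (any AE) | 0.897 + 0.1×0.103×0.1 = 89.8% | 0.897 + 0.4×0.103×0.3 = 90.9% |

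The any-AE row can hardly move. Rows for single terms and for maximum grade can.

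**The case against.** **Tabulation by randomized group is legitimate.** It describes a strategy: start on this regimen and escalate if needed. The groups are defined as subjects randomized to each regimen, the protocol prescribes the layout, and nothing is tested. This stands, and it is why the whole-period tables should be kept. It does not give the profile of 40 mg b.i.d. or 80 mg q.d. alone, which is what those headings suggest.

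**Much is already separated.** A reader might infer that the SAP has no escalation-specific safety analysis, or that SAE and discontinuation rates cannot be disentangled. The documents do not support that: SAP 2.7 includes a summary of never-escalated subjects and a before/after split for the most serious categories, and ECG is covered. What remains is that SAP 2.7 does not say the split is shown by regimen, and that the other tables have none.

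**The number affected may be small.** At a 33% MMR rate, 156 × 0.67 gives about 105 non-responders, and it is tempting to treat them all as candidates for escalation. They are not. The count includes patients who stopped early or have no Week 48 PCR (SAP 2.5.3 and 2.5.4). Protocol 9.1.1 directs discontinuation for treatment failure, with an exception, and Protocol 6.6.2 bars escalation after specified toxicity. Later loss of MMR adds some patients back. No escalation rate follows from the documents.

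**A different effect in each arm is not shown.** Allocation is 1:1 and Protocol 4.2 predicts similar efficacy for the two regimens. A difference is possible but unsupported.

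**200 mg may be no less safe.** Protocol 4.2 regards its safety as comparable, on 12 patients. Unmixed tables would let the trial examine that.

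**Conclusion.** The point holds as a cheap improvement to descriptive safety reporting. The main by-regimen AE tables, and any by-regimen laboratory worst-value summaries, mix 80 mg and 200 mg exposure, and the existing escalation tables close only part of the gap.

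The size is unknown. What the documents fix is the ceiling per escalated patient: 84 of 144 weeks for escalation at Week 60, falling to 24 at Week 120. The incidence shifts in the illustration rest wholly on assumed escalation and event rates.

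The 96-week and end-of-treatment analyses are most exposed. A reader might infer that the 48-week analysis is free of the problem, or as affected as the later ones; neither follows. It is exposed only for patients who started at least 12 weeks before the last patient and have escalated.

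The primary test, its power and its confidence interval are untouched.

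**What to change.** In SAP 2.7 and 2.7.1:

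1. Add by-regimen tables for every AE category in 2.7.1, and for the laboratory worst-grade and worst-value summaries in 2.7.3, that stop the day before the escalation start date. SAP 2.1.1 already derives that date. Protocol 10.1.1 has a worsened event re-entered with its own start date, so worsening after escalation can be separated.
2. Show later events in a separate post-escalation (200 mg q.d.) column, with exposure time or exposure-adjusted rates.
3. State how events after a return to 80 mg a day are assigned.
4. Keep the whole-period randomized-group tables, labelled as starting regimen with optional escalation.

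ECG needs no change beyond SAP 2.7.4.1.

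**Cost.** One period flag and a few extra tables. By-regimen follow-up becomes shorter and unequal for escalated patients, who are selected for lack or loss of response and for absence of specified toxicity. Crude percentages alone would therefore mislead, which is why item 2 asks for exposure time. Sample size and the primary analysis do not change.

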2.7.1.1 Adverse events of special interest / grouping of AEs

Data analysis of AESIs

An adverse event of special interest (AESI) is a grouping of adverse events that are of scientific and medical concern specific to compound asciminib. These groupings are defined using

MedDRA terms, SMQs (standardized MedDRA queries), HLGTS (high level group terms), HLT (high level terms) and PTs (preferred terms). Customized SMQs (Novartis MedDRA queries, NMQ) may also be used. A NMQ is a customized group of search terms which defines a medical concept for which there is no official SMQ available or the available SMQ does not completely fit the need. It may include a combination of single terms and/or an existing SMQ, narrow or broad. The latest approved version of CRS (Case Retrieval Strategy) prior to the respective database lock will be used.

For each specified AESI, number and percentage of subjects with at least one event of the AESI occurring during the on-treatment period will be summarized.

Summaries of these AESIs will be provided (specifying grade, SAE, relationship, leading to treatment discontinuation, leading to dose adjustment/interruption, death, etc.). If sufficient number of events occurred, analysis of time to first occurrence will be applied.

A listing of all grouping levels down to the MedDRA PTs used to define each AESI will be generated.

2.7.2 Deaths

Separate summaries for on-treatment and all deaths (*including post-treatment deaths*) will be produced on the corresponding Safety set (SAF, SAF 2) by randomized groups, system organ class and preferred term.

All deaths will be listed, where deaths occurring during the post-treatment period will be flagged.

2.7.3 Laboratory data

Clinical laboratory evaluations

All laboratory data will be summarized by visit/time. Shift tables using the low/normal/high/ (low and high) classification will be used to compare baseline to the worst on-treatment value.

Grading of laboratory values will be assigned programmatically as per NCI Common Terminology Criteria for Adverse Events (CTCAE) version 5. The calculation of CTCAE grades will be based on the observed laboratory values only, clinical assessments will not be taken into account.

CTCAE Grade 0 will be assigned for all non-missing values not graded as 1 or higher. Grade 5 will not be used. Details of CTCAE grading and imputation rules are presented in [Appendix 5.3](#).

For laboratory tests where grades are not defined by CTCAE version 5.0, results will be categorized as low/normal/high based on laboratory normal ranges.

On analyzing laboratory data, all sources (central and local laboratories) will be combined. The summaries will include all assessments available for the lab parameter collected no later than 30 days after the last study treatment administration date.

The following summaries will be generated on the corresponding Safety set (SAF, SAF 2) separately for hematology, and biochemistry laboratory data (by laboratory parameter):

- Worst post-baseline CTCAE grade (regardless of the baseline status). Each subject will be counted only for the worst grade observed post-baseline in the on-treatment period.
- Shift tables using CTCAE grades to compare baseline to the worst on-treatment value.
- For laboratory tests where CTCAE grades are not defined, shift tables using the low/normal/high/(low and high) classification to compare baseline to the worst on-treatment value.

The following listings will be produced separately for hematology and biochemistry for the laboratory data:

- Listings of all laboratory data, with CTCAE grades and classification relative to the laboratory normal range. Lab data collected during the post-treatment period will be flagged.
- Listing of all CTCAE grade 3 or 4 laboratory toxicities

Liver function parameters

Liver function parameters of interest are total bilirubin (TBL), Alanine aminotransferase (ALT), Aspartate aminotransferase (AST) and alkaline phosphatase (ALP). The number (%) of subjects with worst post-baseline values as per Novartis DILI Clinical safety guidelines will be summarized for the criteria defined by single lab parameter. For combination of various parameters, the worst post-baseline values from each single parameter are taken into consideration, i.e. it may not come from the concurrent measurement (i.e. same assessment).

The following summaries will be produced:

- ALT or AST > 3x upper limit of norm (ULN)
- ALT or AST > 5xULN
- ALT or AST > 8xULN
- ALT or AST > 10xULN
- ALT or AST > 20xULN
- TBL > 2xULN
- TBL > 3xULN
- ALT or AST > 3xULN & TBL > 2xULN
- ALT or AST > 3xULN & TBL > 2xULN & ALP \geq 2xULN
- ALT or AST > 3xULN & TBL > 2xULN & ALP < 2xULN

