1. ***pre-treatment period:*** from day of subject’s informed consent to the day before first administration of study treatment
2. ***on-treatment period:*** from date of first administration of study treatment to 30 days after date of last administration of study treatment (including start and stop date).
3. ***post-treatment period:*** starting at day 31 after last administration of study treatment.

If dates are incomplete in a way that clear assignment to pre-, on-, post-treatment period cannot be made, then the respective data will be assigned to the on-treatment period.

Safety summaries (tables, figures) on the corresponding Safety set include only data from the on-treatment period with the exception of baseline data which will also be summarized where appropriate (e.g. change from baseline summaries). In particular, summary tables for adverse events (AEs) will summarize only on-treatment events, with a start date during the on-treatment period. In addition, a separate summary for death will be provided.

However, all safety data (including those from the pre-treatment and post-treatment) will be listed and flagged as appropriate.

Efficacy summaries on the FAS and FAS 2 (apart from OS and PFS) include data from baseline up to either the last assessment on or before the End of Treatment (EoT) visit or before or on treatment failure, whichever is the earliest.

The efficacy assessments collected post-treatment failure or post-EoT visit are not included in any efficacy analyses (except for OS and PFS analyses). However, they will be listed and flagged as appropriate.

Windows for multiple assessments

Data such as molecular response, cytogenetic response collected over time (including unscheduled visits) will be summarized by scheduled time point. As subjects do not always adhere to the visit schedule, visits will be remapped according to visit windows defined in Tables 2-1 to Table 2-3 of this document to enable by-visit analysis. Only those protocol-defined visits will have the visit window defined. Each assessment (including the end of treatment assessment), either scheduled or unscheduled, will have a mapped visit assigned, as long as study day is available, according to the defined visit window up to the date with data included.

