A summary table with descriptive statistics for LVEF at different timepoints (screening/baseline, Week 48 (+/- 4 weeks) and end of treatment visit) and for change from baseline will be presented. A shift table for LVEF categories ($\leq 40\%$, 41-49%, $\geq 50\%$) at baseline versus worst value on treatment will also be presented.

ECG assessment needs are similar for all subjects up to week 48.

For subjects with dose escalation, ECG assessments will be performed at:

- on the day of dose escalation (pre-dose and between 2h to 3h post-dose ECGs are required),
- two weeks post-dose escalation,
- at next 2 quarterly visits (at 3 and 6 months post-dose escalation),
- every 6 months thereafter.

The above described analyses for ECG data will also be performed separately for a) subjects by dose escalation status (with or without dose escalation) and for b) only for subjects with dose escalation (prior to and after dose escalation).

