2.7.4.3 Vital signs

Vital sign assessments are performed in order to characterize basic body function. The following parameters were collected: height (cm), weight (kg), body temperature ($^{\circ}\text{C}$), heart rate (beats per minute), systolic and diastolic blood pressure (mmHg).

Data handling

Vital signs collected on treatment will be summarized. Values measured outside of on treatment period will be flagged in the listings.

Data analysis

The number and percentage of subjects with notable vital sign values (high/low) in systolic blood pressure, diastolic blood pressure, pulse rate, weight and temperature will be presented.

A listing of all vital sign assessments will be produced and notable values will be flagged. In the listing, the assessments collected outside of on-treatment period will be flagged.

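### SAP 2.7.3 and 2.7.4.3 omit the escalation split used for ECGs and selected AEs, so laboratory, liver and vital-sign tables pool starting-dose and 200 mg values (minor)

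*SAP*

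**What the plan says.** From Week 60 to Week 120 a subject without MMR, or with loss of it, may move from 80 mg daily to 200 mg q.d. (Protocol 6.3.2, Table 6-2 footnote; Protocol 6.6.2).

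SAP 2.7 plans extra tables by escalation status and, in its own words, "for d) only for subjects with dose escalation (prior to and after dose escalation". They cover four items: deaths; SAEs and AESIs; AEs leading to treatment discontinuation; grade 3 and 4 AEs. SAP 2.7.4.1 adds ECGs: "The above described analyses for ECG data will also be performed separately for a) subjects by dose escalation status (with or without dose escalation", and again before and after escalation.

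The laboratory and vital-sign sections contain no such instruction:

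- SAP 2.7.3 plans a worst post-baseline grade table and "Shift tables using CTCAE grades to compare baseline to the worst on-treatment value".
- For combined liver criteria the same section states that "the worst post-baseline values from each single parameter are taken into consideration, i.e. it may not come from the concurrent measurement".
- SAP 2.7.4.3 plans "The number and percentage of subjects with notable vital sign values (high/low) in systolic blood pressure" and other vital signs.

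The on-treatment period in SAP 2.1.1 runs "from date of first administration of study treatment to 30 days after date of last administration of study treatment", with no break at escalation. Treatment groups are fixed by the starting regimen, for example "Subjects randomized to asciminib 40 mg b.i.d. at the beginning of the study".

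**The concern.** Protocol 3 sets the latest escalation visit at Week 120 so that enough follow-up remains to describe the efficacy and safety of 200 mg. Laboratory changes and vital signs belong to the same secondary safety endpoint as ECGs (Protocol Table 2-1), yet only ECGs are split.

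In an escalated subject, a table built on one worst value over the whole treatment period does not show whether that value arose at the starting dose or at 200 mg. In any table by group, a 200 mg value counts under 40 mg b.i.d. or 80 mg q.d. The data types concerned are relevant ones. In the earlier 200 mg q.d. cohort (n=12, Protocol 4.2), increased lipase, increased amylase, hypertension and hypertriglyceridaemia were each reported as AEs in 33.3% (4/12).

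**Working it through.** The documents give no figure for this point. The only design calculation, 80% power with 156 subjects, reproduces: rejecting at 47 or more of 156 gives one-sided alpha 0.0241 and power 0.801. It is unaffected.

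**Text check**

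| Output | SAP section | Split at escalation? |
|---|---|---|
| Deaths, SAEs/AESIs, AEs leading to discontinuation, grade 3/4 AEs | 2.7 | Yes |
| ECG | 2.7.4.1 | Yes |
| Worst grade and shift tables | 2.7.3 | No |
| Liver thresholds | 2.7.3 | No |
| Notable vital signs | 2.7.4.3 | No |

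After its list, SAP 2.7 refers onward for escalation only to the ECG section.

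**Why the AE split does not replace the missing one.** Under Protocol 10.1.1 an abnormal laboratory value is an AE only if it causes signs or symptoms, is judged clinically significant or needs therapy. The grades in the SAP 2.7.3 tables come from the values alone. The two sources therefore count different things.

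**Combined liver criterion.** Because worst values need not be concurrent, ALT above 3xULN on 80 mg and bilirubin above 2xULN on 200 mg in one subject count as one combined case.

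**How much time is pooled** (escalated subject, 144 weeks completed, no de-escalation):

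- Escalation at Week 60: (144 − 60)/144 = 84/144 = 58% of dosing time at 200 mg.
- Escalation at Week 120: (144 − 120)/144 = 24/144 = 17%.
- With the 30-day tail (4.3 weeks): 88.3/148.3 = 60% and 28.3/148.3 = 19% of the on-treatment period.
- At 96 weeks on treatment: 36/96 = 38% (escalated at Week 60) or 12/96 = 13% (escalated at Week 84).

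The 48-week analysis can be touched too. Its cut-off is 48 weeks after the last subject's first treatment and it uses all data to that date (SAP 2.1), so anyone first treated at least 12 weeks before the last subject can have reached Week 60.

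**Scheduled measurements before/after escalation** (Protocol Table 8-1, post-dose visits from Week 2). Chemistry: 8/8 for escalation at Week 60 (Weeks 2, 4, 8, 12, 24, 36, 48, 60; then 62, 72, 84, 96, 108, 120, 132, 144) and 13/3 for Week 120. Blood pressure is not scheduled at the two-week visit, which gives 8/7 and 13/2.

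**What pooling loses** (assumed rates, independent periods). The pooled rate is 1 − (1 − a)(1 − b). With a = 5% at the starting dose and b = 20% at 200 mg it is 1 − 0.95 × 0.80 = 24%. With the two rates exchanged it is also 24%.

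**Effect on a whole table** (assumed 10% at the starting dose and 20% at 200 mg, so 28% pooled in escalated subjects). With 10 of 156 escalated: (146 × 0.10 + 10 × 0.28)/156 = 11%. With 60 escalated: (96 × 0.10 + 60 × 0.28)/156 = 17%. Without escalation it would be 10%.

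**The case against.** The case against has five parts.

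1. *These are descriptive tables, the protocol's own laboratory and vital-sign plan (Protocol 12.5.2) has no split, and values can be traced.* This stands. SAP 2.7.3 lists all laboratory values and all grade 3/4 toxicities, SAP 2.7.4.3 lists all vital signs, SAP 2.4.1 lists all doses, and SAP 2.1.1 defines a study-day reference at the first escalated dose. The gap is only against the SAP's own treatment of AEs and ECGs.

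2. *Serious problems are already split.* This also stands. The SAP 2.7 items carry no relatedness condition, so unrelated grade 3/4 AEs are covered. Liver cases confirmed on repeat without another cause are reported as SAEs (Protocol 6.6.4.1) and are covered too. Before escalation, "there must not be any grade 3 or 4 toxicity while on therapy, or persistent grade 2 toxicity, possibly related to asciminib"; the rule refers to toxicity that best management has not resolved. A related grade 3/4 value at the starting dose is thus unlikely in an escalated subject. The stated exception is a subject whose dose was reduced, whose event has resolved and who has had at least 3 months on 80 mg.

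3. *ECGs have their own escalation schedule (Protocol 8.4.3), which explains the difference.* This holds only in part. Haematology and chemistry are also drawn at the two-week post-escalation visit. The argument is better for vital signs, which are not scheduled there but are measured at the 12-weekly visits.

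4. *A before/after split is not dose attribution.* Correct. Subjects may return from 200 mg to 80 mg, and may have been on 40 mg earlier (Protocol 6.6.2 and 6.6.3).

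5. *The split can suggest a dose effect that is not there.* Correct. Assume the same weekly risk of a related grade 3/4 value at both doses, 10% over 60 weeks. Eligibility makes the before rate about 0%, while the after rate is 1 − 0.90^(84/60) = 14% over 84 weeks or 1 − 0.90^(24/60) = 4% over 24 weeks. With 5% the after figures are 7% and 2%; with 20% they are 27% and 9%. A footnote is needed.

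**Conclusion.** The omission and the pooling are confirmed from the text. The consequence is minor. It concerns descriptive worst-grade, shift, liver-threshold and notable-vital-sign tables in escalated subjects, and mainly values not captured as grade 3/4 AEs, SAEs, AESIs or AEs leading to discontinuation. Non-escalated subjects and by-visit results through Week 48 are unaffected. Later by-visit laboratory summaries mix doses across subjects, not within one. No test, primary result or dosing rule changes.

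The number of values affected cannot be computed, because neither the number escalating nor the rates at 80 mg are given. The time shares assume completion without de-escalation, and the rate examples use assumed inputs.

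Two stronger readings are tempting but not supported. A reader might infer that 200 mg toxicity will be hidden. The severe, serious and treatment-ending AEs are already shown before and after escalation, and every value is listed. A reader might also use the 12-subject cohort to count how many 200 mg events the existing split would miss. AESIs of any grade are split, and the AESI list is not in these documents, so that count has no firm basis.

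**What to change.** Extend items c) and d) of SAP 2.7 to the worst-grade, shift and liver tables of 2.7.3 and the notable-value table of 2.7.4.3, using the escalation start date already derived in SAP 2.1.1.

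- Keep the existing pre-treatment baseline, as the SAP does for the outputs it already splits. A new reference at escalation could hide an abnormality already present on the starting dose.
- Keep the overall tables and, in them, the present liver rule. In the before/after tables, assess combined liver criteria within each period.
- Show exposure time per period.
- Add a footnote that the comparison is descriptive, because escalation selects subjects without significant related toxicity, follow-up is unequal, and the after period may include de-escalated dosing.

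The cost is SAP wording and a re-run of existing table programs with a period variable. No new data are needed. The downside is a few more tables, some of them sparse.
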